Effects of an Acute Bout of Moderate-Intensity Aerobic Exercise And High-Intensity Intermittent Exercise On Sleep During Night Shifts In Medical Shift Workers With Sleep Impairment: A Single-Blind Crossover Randomized Controlled Trial

Document Date: Oct 2, 2024

IRB approved Date: Oct 1, 2024

Project summary

This study aimed to explore the effects of a single bout of moderate- aerobic continuous exercise (MACE) and high-intensity intermittent exercise (HIIIE) on sleep during continuous night shifts in medical shift workers with mild sleep impairment. Medical staff with sleep disturbances due to their night-shift work were randomized to either a treadmill walking session for 47 minutes with moderate intensity (the heart rate reaches 70~75% of the maximum heart rate), treadmill running section for 28 minutes with intermittent high-intensity (the heart rate reaches 90~95% of the maximum heart rate for 4 minutes and 50~70% for 3 minutes), or a quiet-rest control, 14 hours before undertaking a continuous night shift. Sleep quality was assessed by ActiGraph with subjective questionnaire for 1 night and 3 nights after exercise. Tests were performed (t-tests or χ^2 tests) to test for differences between any two of the three intervention trials.

Introduction

Sleep impairment is a common problem among night shift workers (1-3). The prevalence of insomnia in shift workers ranged from 12.8% to 76.4%, higher than estimated for the general population. Moreover, a higher prevalence was observed among women(4, 5). Associations between sleep impairment and deleterious health outcomes have been established, including increased risk of mortality(6, 7), diabetes(8), metabolic syndrome(9), dementia(10), depression, and anxiety(11), as well as impaired quality of life(12). Sleep problems resulting from day and night shifts [5] and the nature of these shifts also contribute to the development of metabolic syndrome(13). The health risks associated with day and night shifts for healthcare workers have been well documented(2, 14, 15), which in turn has led to a reduction in the retention rate of

healthcare workers who work shifts(16). Furthermore, the global demand for shift workers is increasing(17), and shift workers other than healthcare workers will also encounter such health problems.

In contrast, exercise has various health benefits, such as reducing the risk of cardiovascular disease and diabetes(18-20), and improving mental health(21, 22). Additionally, several reviews suggest that exercise effectively improves sleep quality and reduces sleep complaints(23-26). A scoping review demonstrated that diverse types of physical activity were effective for improving sleep in many populations, even in the elderly and in co-morbid or perinatal populations(27). However, little research has been conducted on shift worker populations.

Previous research tended to focus on the effects of regular exercise on sleep outcomes(27, 28). Despite the efforts of the World Health Organization (WHO) and countries around the world to promote exercise(29), regular exercise is still challenging for many middle-aged people with busy families and jobs, or even medical staff who work day and night shifts. In recent years, it has been estimated that over 70% of the global population has failed to achieve the weekly exercise recommendations set forth by the World Health Organization (WHO)(30). It is reasonable to assume that if a single bout of exercise can alleviate the sleep disturbance caused by night shift work, it would be significant benefit to night shift workers who may not have the time or resources to engage in regular exercise. A meta-analytic review revealed that both acute and chronic exercise increased slow wave sleep (SWS) and total sleep time, decreased sleep onset latency and REM sleep(31). Furthermore, research has shown that single exercise sessions comprising light or moderate aerobic exercise and HIIIE are conducive to improved sleep quality(32, 33). Nevertheless, no studies have been conducted to

investigate the effects of a single session of MACE and HIIIE on the sleep of night-shift workers.

Several studies have demonstrated that HIIT can significantly increase ‘excess post-exercise oxygen consumption’ (EPOC)(34, 35). A systematic review showed that for the same energy expenditure of continuous and intermittent exercise, intermittent exercise produced higher EPOC than continuous exercise, and these data suggest that for a given energy expenditure, intermittent exercise may be more effective than continuous exercise in reducing body fat(36). Therefore, this study hypothesizes that higher EPOC with greater energy consumption may assist night shift workers to achieve better sleep.

This study aimed to investigate whether a single session of MACE or HIIIE would have a favorable impact on the sleep of night shift workers over the subsequent days.

2. Methods

2.1. Design

The study was conducted in a single-blind, repeated-measures, three-armed crossover design, and participants were randomly assigned to the MACE trial, the HIIIE trial, and the control (COL) trial for the survey, with a minimum of 21 days between the three trials. To eliminate the impact of individual physical differences, a crossover trial was conducted with the same group of subjects. This study compared MACE, HIIIE, and a controlled trial to determine the effects of different exercises on subjective, objective sleep quality, and autonomic nervous activity in workers engaged in night shift work. The primary outcome was the results of subjective and objective sleep quality, and the secondary outcome was autonomic nervous activity. The study started on 10/12/2022 and ended on 31/08/2024.

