2.3.2. Measure Of Sleep

Participants wore a wrist ActiGraph (wActiSleep, Pensacola, Florida, United States) on the nondominant hand 4 sleep periods from the sleep before exercise to the sleep third sleep after exercise intervention (before the third night duty). The sleep data were obtained from ActiGraph monitors and analyzed by ActiLife software version 6 using the Cole-Kripke algorithm, including eight sleep indices (sleep latency, total counts, sleep efficiency, total sleep time [TST], wake after sleep onset [WASO], number of awakenings, length of awakenings, time in bed)(49, 50). Participants also recorded the time they went to bed and woke up to enable coordinate checks with the actigraphic data. Daily sleep quality was measured using a question that was chosen because it was easy to conceptualize, simple to understand, and less burdensome for participants. The question asked was: On a scale of 0-10, with 0 being the worst sleep and 10 being the best, rate the quality of the previous sleep(51).

Participants self-reported age, marital status, exercise habits, smoking, caffeine and alcohol consumption, and chronic diseases. Height and weight were measured from which body mass index (BMI) was calculated as weight in kilograms divided by the square of height in meters (kg/m²).

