2.4. Statistical Analysis

Descriptive statistics of data use median and interquartile range (IQR) to describe the distribution of continuous variables. This method is effective in describing the

concentration trend and the degree of variability of the data, and is particularly suitable for data with a non-normal distribution.

The between-exercise factor was intervention (MACE, HIE and control trials) and the within-subjects factor was time points were analyzed. The Wilcoxon signed-rank test is used to compare data between two groups. This test is a non-parametric method for comparing the median difference between two related samples or pairs of data that can be analyzed without assuming that the data conform to a normal distribution.

All statistical tests were performed using the two-tailed test with a significance level (α) of 0.0 which were performed with SAS software (version 9.4; SAS Institute Inc., Cary, NC, USA).

Reference

6. Huang B-H, Duncan MJ, Cistulli PA, Nassar N, Hamer M, Stamatakis E. Sleep and physical activity in relation to all-cause, cardiovascular disease and cancer mortality risk. *British journal of sports medicine.* 2022;56(13):718-24.
7. Chen L-J, Hamer M, Lai Y-J, Huang B-H, Ku P-W, Stamatakis E. Can physical activity eliminate the mortality risk associated with poor sleep? A 15-year follow-up of 341,248 MJ Cohort participants. *Journal of sport and health science.* 2022;11(5):596-604.

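### The primary outcome is a domain, not a variable: roughly 36 to 81 candidate primary results fit the text, depending on the reading, and none is singled out

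*Protocol*

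**What the plan says.** Protocol section 2.1 (Design) states: "The primary outcome was the results of subjective and objective sleep quality, and the secondary outcome was autonomic nervous activity".

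The measures are in section 2.3.2 (Measure Of Sleep). The objective part is the ActiGraph output, "including eight sleep indices": latency, total counts, efficiency, total sleep time, wake after sleep onset, number of awakenings, length of awakenings and time in bed. The subjective part is a single daily rating from 0 to 10. No measure is put ahead of another.

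The timing is described in two ways. Section 2.3.2 has the watch worn for "4 sleep periods from the sleep before exercise to the sleep third sleep after exercise intervention", that is, one sleep before and three after. The Project summary says: "Sleep quality was assessed by ActiGraph with subjective questionnaire for 1 night and 3 nights after exercise".

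On contrasts, the Project summary tests are "to test for differences between any two of the three intervention trials". The aim at the end of the Introduction asks only whether either exercise session benefits sleep over the following days. Section 2.4 mentions two factors ("The between-exercise factor was intervention (MACE, HIE and control trials) and the within-subjects factor was time points were analyzed"), but the only test it names is pairwise: "The Wilcoxon signed-rank test is used to compare data between two groups".

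The sample-size sentence in section 2.2 refers to a sleep outcome without naming it. Sleep efficiency and the AIS-5 are singled out in section 2.2, but only as entry criteria.

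**The concern.** A primary endpoint should say in advance which single result, or which stated combination, decides whether the intervention worked. Here every ingredient is listed (measures, sleeps, contrasts) and none is chosen. The word joining subjective and objective can mean that both are required or that either will do.

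A primary claim made on this wording could rest on any of dozens of results. With 14 analysed participants and pairwise tests, some of those are likely to fall below 0.05 by chance. A reader of the trial report could not tell a planned result from the most favourable of many.

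Timing adds to this. The version at hand is dated Oct 2, 2024, and section 2.1 gives the study end as 31/08/2024. On its own, this document cannot show that a measure and a sleep were selected before results could be seen.

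**Working it through.** **Plan's own figure.** The protocol states no number of primary tests, so there is none to reproduce. Its one design figure, 12 per group in section 2.2, comes with no numerical effect size and no named variable. It neither identifies a primary measure nor enters this check.

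**Count.** Formula: measures × post-exercise sleeps × contrasts.

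- Measures: 8 + 1 = 9 (section 2.3.2).
- Post-exercise sleeps: 3 (section 2.3.2), or 2 on one reading of the Project summary.
- Contrasts: 3 (Project summary), or 2 if only exercise versus control answers the aim in the Introduction.

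Results: 9 × 3 × 3 = 81; 9 × 2 × 3 = 54; 9 × 3 × 2 = 54; 9 × 2 × 2 = 36.

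**Chance of at least one false positive if any one result suffices.** The level is assumed to be 5%: section 2.4 prints it as 0.0, and section 2.2 mentions 5% for the sample size. For independent tests, 1 − 0.95^k gives 84.2% (k = 36), 93.7% (k = 54) and 98.4% (k = 81). These are ceilings, because sleep indices from one watch are related.

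A null simulation handles the dependence. It uses the exact two-sided Wilcoxon signed-rank test at n = 14 (attained size 0.0494), three trials per participant and contrasts that share trials. The protocol gives no correlations, so they are assumed. Each range spans two structures: one common correlation, or measure correlation × sleep correlation.

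| Reading | r = 0 | r = 0.5 | r = 0.7 | r = 0.9 |
|---|---|---|---|---|
| 81 (3 sleeps, 3 contrasts) | 97% | 84-89% | 67-76% | 41-47% |
| 54 (2 time points, 3 contrasts) | 91% | 75-79% | 60-65% | 38-41% |
| 54 (3 sleeps, 2 contrasts) | 92% | 74-80% | 57-65% | 33-38% |
| 36 (2 time points, 2 contrasts) | 82% | 64-68% | 49-55% | 30-32% |

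Over r = 0.5 to 0.9 this is about 30-90%. A cruder model that sets every pair of tests at 0.9, across contrasts as well, gives 20-21%. It understates the risk: with equal variances, two contrasts sharing a trial correlate at only 0.5 in size for the same measure.

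**If the rating and an objective index are both needed** (r from 0 to 0.9 unless stated):

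- At any sleep and contrast: 17-32% with three contrasts, 12-22% with two.
- At the same sleep and contrast: 9-21% with three, 6-16% with two.
- Same sleep, contrast and direction: about 4-8% at r = 0, but 9-21% at r = 0.5-0.9 (two or three contrasts).
- Both favouring exercise over control at the same sleep: about 2-8%, against a one-direction benchmark of 2.5%.

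**Comparator.** One variable at one time with three contrasts gives 12.5% unadjusted and 4.6% with Holm.

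**The case against.** Several points on the other side have force.

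*The count is not a fixed number.* A reader might infer that the lists yield 54 to 81 tests. That presumes the comparison of the two exercise types is primary, and the aim in the Introduction does not need it. Without it the count runs down to 36. Treating all nine measures as primary is also an upper-end reading: time in bed and total counts are not plainly measures of sleep quality. This stands, so the count is given as a rough range.

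*Requiring both parts may control the error.* A reader might infer that the false-positive chance is far above 5% even then. That holds when the two results may come from any sleep and contrast. It does not hold on the strictest readings: same sleep, contrast and direction with nearly uncorrelated measures, or a claim limited to benefit over control. The protocol adopts none of these readings, so they do not cure the ambiguity.

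*The percentages rest on assumptions.* Correlations and the 5% level are assumed, and the simulation ignores ties, which a 0-10 rating in 14 people will produce. The Project summary attaches its pairwise comparisons to t-tests or χ² tests, whereas section 2.4 names Wilcoxon. The sizes are therefore illustrative; the missing choice does not depend on them.

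*The SAP may deal with multiplicity.* It may, and it was not available. The absence of an adjustment rule here is no finding. Choosing the primary variable, however, is a protocol decision, which section 2.1 makes and makes badly.

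*The dates.* A reader might infer that the endpoint was picked after the data were seen. The document does not support that: it dates this version only, and earlier versions are not shown.

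**Conclusion.** The point holds and needs correcting before any primary claim is made. Section 2.1 fixes a domain as primary. Roughly 36 to 81 results qualify, depending on how sleeps and contrasts are read, and no rule joins the subjective and objective parts.

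If any one result suffices, unadjusted at an assumed 5%, the chance of a false primary claim is about 30-90% for assumed correlations of 0.5-0.9. If the rating and any objective index are both needed, at any sleep and contrast, it is about 12-32%. The rate comes near nominal only under stricter readings that the text does not state, and then only if measures are nearly uncorrelated or the claim is confined to benefit over control.

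The conclusion that no single result decides the trial rests on the text alone. The percentages rest on the stated assumptions and would fall if an unseen SAP already controls the error.

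**What to change.** In section 2.1:

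1. Name one primary variable at one time, either a single post-exercise sleep or the mean of the post-exercise sleeps. Alternatively, name one objective and one subjective variable and state whether both must be positive or either is enough.
2. State which contrasts are primary and hold the overall error at 0.05 across them, for example with Holm, unless the SAP already does so.
3. Label all other indices and sleeps secondary or exploratory.
4. State when the choice was made. If a choice independent of the results cannot be shown, report the sleep results as exploratory.

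No new data are needed. The cost is some power and a less favourable label. At n = 14 with normal differences, the standardised paired difference (dz) detectable with 80% power rises from about 0.83 for one unadjusted Wilcoxon test to about 0.95 under Holm over three contrasts. At dz 0.83, power falls from 80% to about 66-67%. With two variables that must both be positive, the detectable dz is 1.01-1.08 (assumed correlation 0.9 down to 0). If either is enough, so that there are six tests, Holm's strictest step needs 1.13.

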2.2. Participants

Potential participants were recruited from six hospitals in central Taiwan through hospital and internet advertisements. Only women were recruited in this study because previous research indicates more sleep difficulties in females than in males. Those who were interested in the study were invited to attend an orientation meeting if they met the following eligibility criteria: medical staff who have worked at least three consecutive night shifts; reporting sleep disturbed during the night shift; age between 20 and 64 years; not taking sleep/psychotropic medications; no clinical diagnosis of sleep apnea or other sleep disorder; and not exercising regularly (ie, below 60 minutes per week). Twenty-six medical staff participated in the preliminary meeting, at which the researchers described the study purpose, procedure, and the exercise program and rest condition. These potential participants completed the Satisfaction with Life Scale (SWLS) and initial sleep assessments. The SWLS is a simple self-administered psychometric properties questionnaire to examine the mental health of individuals and the possible risk of depression or other psychiatric diseases(37-39). The initial sleep assessment was made through the Chinese version of the self-reported 5-item Athens Insomnia Scale (AIS-5)(40), and sleep recording watch ActiGraph (wActiSleep, Pensacola, Florida, United States) on the nondominant hand for 4 nights just before night shifts. This study aimed to investigate the effects of a single session of exercise on individuals with sub-optimal sleep quality; thus, individuals were included if they scored above 5 on the AIS-5(40) or had a sleep efficiency below 85%(41) before their first night shift. Among the 26 potential participants, 3 did not meet the criteria and 4 decided not to attend the study. Finally, of the 19 subjects, 1 withdrew after the MACE trial, 2 withdrew after the controlled trial, and 2 withdrew after both the MACE trial and the controlled trial because they could not fit into the schedule, resulting in a sample

size of 14 participants. A simple randomization method was used to randomize participants into three groups using Microsoft 365-Excel (Microsoft, Redmond, Washington, United States). They were randomly assigned to either a MACE-HIIE-control ($n = 5$), HIIE-control-MACE ($n = 5$), or control-MACE-HHIT ($n = 4$), as shown in Figure 1. All participants were aware of their group assignment. Participants who attended the study were rewarded with TWD 2500 (approximately USD 78). All participants completed the study. Previous research has indicated a minimum of 12 participants per group is able to detect a small effect size of physical activity on sleep outcome with setting beta at 20% and alpha at 5% (32, 42, 43). The study was approved by the institutional review board of China Medical University Hospital, Taiwan (CMUH111-REC2-186), and the study was performed in accordance with good clinical practice and the ethical standards as laid down by the Declaration of Helsinki. Written and informed consent was obtained from all subjects at the beginning of the study.

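### Twelve participants are said to detect a small effect with 80% power; with 12 to 14 women in this crossover, power for a conventional small effect is about 10%

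*Protocol*

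**What the plan says.** Protocol section 2.2 (Participants) justifies the size in one sentence. It credits earlier research, with three citations, for the statement that "a minimum of 12 participants per group is able to detect a small effect size of physical activity on sleep outcome". The error rates attached to it are 5% for alpha and 20% for beta. It gives no numerical effect, standard deviation, within-woman correlation, test or calculation for this trial.

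The same section reports a final "size of 14 participants", in sequence groups of 5, 5 and 4. Section 2.1 describes a three-condition crossover in which the same women receive MACE, HIIIE and control. In section 2.4, "The Wilcoxon signed-rank test is used to compare data between two groups", and "All statistical tests were performed using the two-tailed test".

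**The concern.** Twelve is a very small number for a small effect at 80% power, even when each woman is her own control. The phrase "a minimum of 12 participants per group" also does not fit a crossover: there are no treatment groups of 12, only 14 women who each receive all three conditions. The figure appears to have been carried over from other studies without being worked out for this design and test.

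The claim affects how the results are read. If the trial is taken as able to find small effects, a non-significant MACE or HIIIE comparison looks like evidence that a single bout does nothing useful. If it can reliably find only much bigger differences, the same result says little about small ones.

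**Working it through.** **Inputs.** Alpha 0.05 and power 0.80 (section 2.2); two-sided testing and pairwise paired comparisons (section 2.4); n = 12 as claimed and n = 14 as achieved (section 2.2). The protocol does not quantify small. I assume the conventional standardised value of 0.2 and vary its meaning below.

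**Step 1: try to reproduce the claim with a paired comparison.** Let dz be the mean within-woman difference divided by the standard deviation of those differences. Paired t-test power is the probability that a noncentral t with n − 1 degrees of freedom and noncentrality dz·√n falls outside ±t(0.975, n − 1).

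| | n = 12 | n = 14 |
|---|---|---|
| Noncentrality, 0.2·√n | 0.693 | 0.748 |
| Critical t | 2.201 | 2.160 |
| Power at dz = 0.2 | 9.7% | 10.7% |
| Power at dz = 0.5 | 35% | 41% |
| dz with 80% power | 0.89 | 0.81 |

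The claimed 80% is not reproduced. A simulated exact Wilcoxon signed-rank test with normal differences gives about 8% (n = 12) and 10 to 11% (n = 14) at dz = 0.2. With 14 women it reaches 80% at dz of about 0.83.

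**Step 2: the number needed.** The normal approximation gives (1.960 + 0.842)² / 0.2² = 7.85 / 0.04 ≈ 196. The noncentral t gives 199 women (80.0% is just missed at 198).

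**Step 3: let small mean 0.2 of the between-woman standard deviation.** Then dz = 0.2 / √(2(1 − r)), where r is the correlation between two conditions in the same woman. The protocol gives no r, so a range is shown.

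| r | dz | Power, n = 12 | Power, n = 14 |
|---|---|---|---|
| 0 | 0.141 | 7% | 8% |
| 0.5 | 0.200 | 10% | 11% |
| 0.7 | 0.258 | 13% | 15% |
| 0.8 | 0.316 | 17% | 20% |
| 0.9 | 0.447 | 29% | 34% |
| 0.95 | 0.632 | 52% | 59% |
| 0.97 | 0.816 | 73% | 81% |

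Reaching 80% needs r of about 0.975 with 12 women and 0.970 with 14.

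**Step 4: other readings.**

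- Two parallel groups of 12, d = 0.2, two-sided: 7.6%. About 393 per group would be needed for 80%.
- One-sided paired test, which section 2.4 excludes: 16.0% (n = 12) and 17.5% (n = 14).
- Repeated-measures ANOVA over three conditions, f = 0.10: 10% (n = 12) and 11% (n = 14) at r = 0.5; 34% and 39% at r = 0.9.
- Pooled repeated-measures model with 12 measurements per woman (3 conditions × 4 sleep periods), f = 0.10, r = 0.9: 68% and 77%.

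**Step 5: sensitivity if three pairwise contrasts share alpha.** At 0.05 / 3 = 0.0167 per contrast and n = 14, the dz with 80% power rises from 0.81 to 0.97.

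**The case against.** The sentence reports what earlier studies found and does not say outright that this trial has 80% power. Those studies are not at hand, and the claim may be right for their designs. For example, a group-by-time model with three separate groups of 12, four time points, f = 0.10 and r = 0.9 gives about 80%. Section 2.4 also mentions an intervention factor and a time factor, so a pooled model is not wholly foreign to the document. This explains where the number might come from, but it does not make it apply here. The sentence is the protocol's only reason for its size, and the one comparison method section 2.4 specifies is a paired Wilcoxon test in the same women.

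Two cautions stand:

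- The figure of about 10% depends on the assumed meaning of small, and higher values follow if r is very high.
- The detectable 0.81 is large only on the within-woman difference scale. On the between-woman scale it equals 0.81·√(2(1 − r)), that is 0.63 at r = 0.7, 0.51 at r = 0.8 and 0.36 at r = 0.9. Even so, it falls to 0.2 only at r of about 0.97.

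It is also true that the trial ended in August 2024, so its size is settled, and that nothing in the protocol says a null result will be read as no effect. That limits the remedy to wording but leaves the statement incorrect.

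**Conclusion.** The concern holds. For the stated crossover and two-sided paired test, 12 to 14 women do not have 80% power for a small effect. Power is about 10% at dz = 0.2, against a claimed 80%, and 199 women would be needed. With 14 women, 80% power is reached at dz of about 0.81 (t-test) or 0.83 (Wilcoxon).

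This rests on taking small as 0.2, on roughly normal differences, and on the 5% level in section 2.2. Defining 0.2 on the between-woman scale changes the conclusion only if r is about 0.97 or more. The finding concerns the claim as this protocol uses it; whether the cited studies support it in their own settings was not examined.

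**What to change.** Delete the sentence in section 2.2 and replace it with a statement of what the design can detect, for example:

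> With 14 completers, a paired two-sided 5% comparison has 80% power for a mean difference of about 0.8 standard deviations of the within-woman differences (about 0.97 if three contrasts share alpha by Bonferroni). Power for a difference of 0.2 on that scale is about 10%. Non-significant results will be interpreted from confidence intervals and not as absence of an effect.

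Drop the per-group wording, since all women receive every condition. If a sensitivity on the between-woman scale is wanted, give the correlation it assumes.

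The cost is wording only. No further enrolment and no change to the tests are needed, but the stated sensitivity becomes less favourable.
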